- Uncontrolled intercurrent illness including, but not limited to ongoing or active
 infection (e.g. active or chronic hepatitis B and C), symptomatic congestive
 heart failure, unstable angina pectoris, or psychiatric illness/social situations that
 would limit compliance with study requirements

	 History or current status of immune system abnormalities such as hyperimmunity (e.g., autoimmune diseases) that needed to be treated by systemic therapy, such as immuno-suppressants and hypoimmunity (e.g., myelodysplatic disorders, marrow failures, AIDS, transplant immunosuppression). Receiving ongoing treatment with immunosuppressive drugs, or 		
	dexamethasone > 4mg		

Pilot randomized pre-surgical evaluation of varillumab on IMA950 vaccine plus poly-ICLC in patients with WHO grade II low-grade glioma

- 1) Arm 1: Patients will receive IMA950+poly-ICLC and CDX-1127
- 2) Arm 2: Patients will receive IMA950+poly-ICLC.

Drugs included in the current regimen are: 1) IMA950 peptides; 2) poly-ICLC and 3) CDX-1127. IMA950 and poly-ICLC will be administered as one formulation containing 4.96 mg total IMA950 peptides and 1.4 mg poly-ICLC subcutaneously (s.c.) at sub-inguinal sites. CDX-1127 will be administered intravenously (i.v.) at 3 mg/kg

Pre-surgical phase:

On days -23±2, -16±2, -9±2 and -2 relative to the scheduled surgery: All patients receive s.c. injections of IMA950/poly-ICLC vaccine. The 4th dose of pre-surgery IMA950/poly-ICLC vaccine must be administered between 24-48 hrs prior to scheduled surgery. PBMC sample (60-80 mL/draw) is obtained on the day of the 1st vaccine (on day -23±2); also at the D-23±2 visit, PK samples (1 x 10 cc red top tube/draw) will be collected prior to varlilumab administration and 30 minutes (±5 minutes) after the infusion has ended. For Arm 1 patients, Varlilumab (CDX-1127) will be administered i.v. on the day of the first vaccine immediately following the s.c. vaccination.

Surgery: The resected tumor tissue will be sent to the BTRC tumor bank.

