Post-surgery phase: For All patients, at least two weeks after the post-op steroid is tapered, but within 10 weeks post-surgery, the IMA950/poly-ICLC vaccines will be resumed and repeated every 3 weeks for 8 doses (Weeks A1, A4, A7, A10, A13, A16, A19 and A22; defining Week A1 as the week of the first post-surgery vaccine dose). The vaccines will be injected s.c. in the upper fronto-medial side of right thigh with 48±6 hours post-vaccination phone assessment. Patients will be evaluated for any possible adverse events (AEs), regimen limiting toxicity (RLT), and clinical response during clinic visits. For Arm 1 patients, Varlilumab (CDX-1127) will be administered i.v. on the day of A1, A7, A13 and A19 vaccines following the s.c. vaccination and PK samples (1 x10 cc red top tube/draw) will be collected prior to varlilumab administration and 30 minutes (+ 5 minutes) after the infusion has ended .

Weeks A1, A13, A19 and A25: PBMC samples (80 mL/draw) will be obtained to monitor induction of anti-IMA950 T-cell responses as well as T-cell and myeloid cell subsets by flow-cytometry.

Post-Op (within 4 weeks before Week A1) Weeks A10 and A25: MRI scans

12 April 2020 Page 11 of 88 confidential

Study Objectives:

Primary (two co-primary endpoints):

Safety: We will evaluate the incidence and severity of adverse events associated with the treatment regime, with an early stopping rule based on the frequency of Regimen Limiting Toxicity (RLT).

Immunological activity. We will determine the magnitude of CD4+ and CD8+ T-cell responses against the IMA950 peptides in pre- and post-vaccine PBMC using a novel, flow-cytometry-based 2D *ex vivo* assay system. We will determine whether Arm 1 patients demonstrate significantly higher magnitude of response compared with Arm 2 patients.

Exploratory

- 1. To evaluate IMA950-reactive T-cell infiltration and CXCL9/10 expression in tumors resected from Arm 1 and Arm 2 patients (We will compare these readouts between the two groups in a preliminary manner and the historical control patients who were enrolled in IRB# 15-17078 vaccine study).
- 2. To evaluate IMA950-reactive T-cell receptor (TCR) clonotypes in tumors resected from Arm 1 and Arm 2 patients (We will compare this between the two groups in a preliminary manner (and the historical control patients who were enrolled in IRB# 15-17078 vaccine study).

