5.5.8 Study Procedures Post-Vaccine Follow-up

All patients, including those who discontinue protocol therapy early, will be followed for response and toxicity assessments until disease progression, start of a new therapy, or for a maximum of 24 months from study registration (whichever occurs earlier). Follow-up visits should be scheduled per standard-of-care for patients with stable WHO grade II glioma without active treatment (every 3 months). As overall survival is an endpoint of the study, subjects who discontinue protocol therapy must continue to be followed (every 3 months) for survival until death or the conclusion of the study.

For any patient with regimen limiting toxicity (RLT), follow-up will continue as medically appropriate for the specific toxicity until resolution to grade 1 or better or 3 months of no change (stabilization).

If treatment is discontinued for progression, the final study visit will be the final off-study visit, providing there is no ongoing grade 2 or greater treatment related toxicity.

- Physical/neurological examination
- Vital signs
- Interval medical history
- KPS
- Review of concurrent medications
- Adverse event assessment
- MRI scan
- Complete blood count (CBC) with differential and platelet count
- Blood chemistry assessment, including:
 - Alkaline phosphatase, aspartate aminotransferase/alanine aminotransferase (ALT/AST), total bilirubin, calcium, blood urea nitrogen (BUN), creatinine, total protein, albumin, random glucose, potassium, sodium, chloride, bicarbonate.

Serum chemistry and CBC tests are required at the first follow-up visit or when previous tests demonstrated any abnormality. If a patient does not show any abnormality during the course or at the first follow-up visit, that patient will not require CBC and chemistry on the follow-up visits per protocol.

12 April 2020 Page 37 of 88 confidential

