8.1 Immunological Monitoring of PBMCs

Analyses of immune responses in PBMC will allow non-invasive evaluation of vaccine-induced immune response. As one of two co-primary endpoints of the current study, we will determine the response rate and magnitude of CD4+ and CD8+ T-cell responses against the IMA950 peptides in pre- and post-vaccine PBMC using a novel, flow-cytometry-based 2D *ex vivo* assay system. We will determine whether Arm 1 patients demonstrate higher response rate and/or magnitude of response compared with Arm 2 patients.

As the primary method of PBMC analysis, we will use a novel 2D multimer staining-based assays. ⁸³ The use of fluorescently labeled MHC multimers has become an essential technique for analyzing disease- and therapy-induced T-cell immunity. However, limitations on available PBMCs from patients preclude a comprehensive analysis of T-cell immunity. To address this issue, Hadrup et al. developed a combinatorial encoding strategy that allows the parallel detection of a multitude of different T-cell populations in a single sample (2D multimer staining-based assays). ⁸³ Detection of T-cells from PBMC by combinatorial encoding is as efficient as detection with conventionally labeled multimers but results in a substantially increased sensitivity and, most notably, allows comprehensive screens to be performed. We have confirmed that we can detect increases of IMA950-specific T-cells using PBMC samples obtained from GBM patients receiving IMA950 vaccines.

As the primary method to evaluate the relative immune response levels between two Arms, the relative magnitude of responses against each of IMA950 antigens will be compared between two Arms by comparing the sum of post-vaccine tetramer+ percentages of all time points from all patients in each of two Arms.

As an exploratory evaluation, a subject will be considered to be an immunological responder, if at any of two consecutive post-vaccine time points (i.e., Weeks A13, 19 and A25):

- 1. Presence of a CD4+ or CD8+ T cell population which shows positive tetramer staining against any of IMA950 antigens.
- 2. Four-fold increase of the frequency of the tetramer positive cells within the CD4+ or CD8+ T cell population at the considered post-vaccination time points versus the prevaccination time point.

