9.2.3 Overall Survival (OS) and Progression-Free Survival (PFS)

PFS is defined as the duration of time from start of treatment to time of progression or death. Patients who have not yet progressed or died will be censored at the time of their last follow-up.

All patients will be followed for a minimum of 2 years, so that their actual 2-year OS and PFS can be determined. OS is defined as the time from start of treatment to time of death. Patients who have not yet died will be censored at the time of their last follow-up.

Tumor recurrence will be assessed minimally at week A25, and patients will be followed with MRI scans and clinical visits as standard of care. Even though we cannot schedule precise time points for follow-up MRIs (because that portion is not a part of the study), we will obtain 2-year PFS as exploratory data. Since LGGs are infiltrative tumors which typically do not enhance with contrast administration, for evaluation of response and PFS,

12 April 2020 Page 64 of 88 confidential

the tumor (i.e., target lesion) will be measured from the T2 or FLAIR MRI images. In case there is an enhancing lesion at the baseline, careful discussion will be made as to whether the pathology information as WHO grade II tumor truly represents the status of the tumor. If the enhancing tumor is still considered to be grade II, the size of the enhancing lesion will be used for evaluation.

9.2.4 Evaluation of PBMC responses against IMA950 in association with OS, PFS and frequency of IMA950 reactive T-cells in the tumor

We will attempt to determine whether vaccine-reactive T-cells in PBMC: 1) correlate with clinical benefits, such as PFS and OS; 2) correlate with observations in the glioma TME; and 3) is higher in Arm 1 over Arm 2 patients.

9.2.5 To tabulate tumor objective response rate (ORR) (According to LGG RANO if there is measurable tumor after surgery).

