- **12.1.5 Exploratory Efficacy Objective:** To estimate overall survival (OS) and progression-free survival (PFS) in the two arms. Product limit (Kaplan-Meier) estimates of the OS and PFS functions will be calculated with 95% Greenwood confidence regions. The trial is not adequately powered for the log-rank test that compares survival functions between arms.
- **12.1.6 Exploratory Efficacy Objective:** Evaluation of PBMC responses against IMA950 in association with OS, PFS and frequency of IMA950 reactive T-cells in the tumor. The association of the immunological parameter with PFS and OS will be evaluated using proportional hazards (Cox) regression. Frequencies will be tabulated.
- **12.1.7 Exploratory Efficacy Objective:** Tabulate tumor objective response rate (ORR). The (multinomial) distributions of responses in patients with measurable tumors (Section 9.2.3) will be calculated with simultaneous (Sison & Glaz) confidence regions. The trial is not adequately powered for a comparison between arms using Fisher's exact test.
- **12.1.8 Exploratory Efficacy Objective:** Evaluation of leukocyte phenotypes in PBMC samples. Frequencies will be tabulated to compare the distributions of the phenotypes between arms.
- **12.1.9 Exploratory Efficacy Objective**: Evaluation of pharmacokinetics for varlilumab. The purpose of this exploratory efficacy objective is to capture minimum and maximum values for the different pharmacokinetics measures. The purpose is not testing hypothesis; therefore descriptive statistics will be reported.

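### The Cox analysis of PFS and OS on immune response (12.1.6) leaves the covariate and its timing undefined; with the plan's own responder rule, response can look protective when it is not

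*Combined protocol and SAP*

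**What the plan says.** Relating the PBMC response to PFS is a named exploratory objective (1.2.4). The analysis is one sentence in 12.1.6: "The association of the immunological parameter with PFS and OS will be evaluated using proportional hazards (Cox) regression". Neither 12.1.6 nor 9.2.4 defines the parameter, names the analysis set, gives a landmark or time-dependent term, or says how patients without later samples are handled.

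Both clocks start at the first dose. Section 9.2.3 states "PFS is defined as the duration of time from start of treatment to time of progression or death" and "OS is defined as the time from start of treatment to time of death".

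Section 8.1 describes two PBMC measures. The responder rule, labelled exploratory, requires its criteria to be met "if at any of two consecutive post-vaccine time points (i.e., Weeks A13, 19 and A25". The magnitude measure is worked out by "comparing the sum of post-vaccine tetramer+ percentages of all time points from all patients in each of two Arms".

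Progression ends treatment (5.10). On visits, 5.5.8 says "If treatment is discontinued for progression, the final study visit will be the final off-study visit", subject to unresolved toxicity. The calendar in Section 6 schedules no research blood after A25.

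**The concern.** Responder status under the 8.1 rule is learned months after the PFS and OS clocks start. To be called a responder, a patient must have stayed on study long enough to give the second sample. One who progresses first is counted as a non-responder or is missing, whatever their immunity. Entered as a fixed covariate from time zero, such a variable credits responders with event-free time that they had to have (guarantee-time bias). A per-patient sum over samples has the same fault, because it grows with the number of samples given.

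This is the plan's only analysis linking the blood immune response to clinical outcome. A hazard ratio well below 1 could be read as evidence that the vaccine response helps.

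**Working it through.** **Sample size.** The plan gives no figure for the Cox analysis. Its only sample-size figure is 15 per arm (12.1.2). With difference 0.8, SD 1.0 and one-sided alpha 0.10, the noncentrality is 0.8/√(2/15) = 2.19 on 28 df, and the power is 81.0% against the stated 80%. It reproduces and gives N = 30.

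**When response can be seen.** The synopsis puts the pre-surgical doses "On days -23±2, -16±2, -9±2 and -2 relative to the scheduled surgery", so the first dose is 23/7 = 3.3 weeks before surgery. After surgery, "within 10 weeks post-surgery, the IMA950/poly-ICLC vaccines will be resumed and repeated every 3 weeks for 8 doses". The upper limit for A1 is therefore 10 weeks; the lower limit of 4 weeks is an assumption. A1 then falls 7.3–13.3 weeks after the first dose. Months are weeks/4.345.

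- A13 (A1 + 12 weeks): 19.3–25.3 weeks, 4.4–5.8 months
- A19 (A1 + 18 weeks): 25.3–31.3 weeks, 5.8–7.2 months
- A25 (A1 + 24 weeks): 31.3–37.3 weeks, 7.2–8.6 months

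On the two-visit reading, confirmation comes at A19 at the earliest, so the guaranteed time is about 6 to 9 months.

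**Early progression.** The only PFS figures in the documents are from the earlier low-grade glioma vaccine study (2.7): median 17 months (range from 10) in newly diagnosed patients and 12 months (range from 3) in recurrent patients. Take A25 at its midpoint of 7.9 months.

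- Exponential, median 12: 1 − 2^(−7.9/12) = 0.37 progress before A25
- Exponential, median 17: 1 − 2^(−7.9/17) = 0.28 (0.27 in the simulation)
- Median 12, none before 3 months: 1 − 2^(−4.9/9) = 0.31
- Median 17, none before 10 months: 0

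**Null simulation (true HR = 1).** True response is independent of PFS; 50% are responders, half confirmed at A19 and half at A25; A1 is uniform over 4–10 weeks after surgery; censoring is at 24 months. PFS hazard ratios, responder against non-responder, from 200,000 simulated patients:

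| PFS pattern | All treated | ≥4 post-surgery vaccines | With A13 sample | A25 landmark |
|---|---|---|---|---|
| Exponential, median 12 | 0.44 | 0.66 | 0.72 | 1.00 |
| Exponential, median 17 | 0.47 | 0.69 | 0.75 | 0.99 |
| Median 12, none before 3 months | 0.55 | 0.65 | 0.71 | 1.01 |
| Median 17, none before 10 months | 1.00 | 1.00 | 1.00 | 1.00 |

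Varying the split of confirmation between A19 and A25 widens the first three rows to about 0.43–0.59 (all treated) and 0.60–0.72 (at least four post-surgery vaccines). With 80% responders the figures are 0.27–0.34 and 0.43–0.48. A summed tetramer percentage under exponential PFS gives 0.44–0.48 per SD in all treated and 0.78–0.81 in the four-vaccine set. A single A13 value, analysed only in patients with that sample, gives about 1.0. So does responder status entered as a time-dependent covariate.

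**At N = 30**, with 50% responders and early events, a falsely protective result (nominal 2.5%) appeared in 29–41% of trials for all treated, 9–16% for the four-vaccine set and 2.8–3.2% at the A25 landmark. With 80% responders the landmark figure is 5.7–6.2%, because the groups are small and unbalanced.

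**Events lost to an A25 landmark.** Divide the share progressing before A25 by the share progressing by 24 months (0.75, 0.62 and 0.80 for the three early-event patterns): 0.37/0.75 = 49%, 0.28/0.62 = 45% (44% unrounded), 0.31/0.80 = 39%. With A25 at its earliest (7.2 months) the last pattern gives 0.276/0.802 = 34%.

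**The case against.** The strongest reply is that the biased analysis is not written down. Section 12.1.6 neither cites the responder rule nor says that the covariate is fixed at baseline or that unsampled patients count as non-responders. The per-patient PBMC measure that the statistical section does define is the standardized pre-to-post difference (12.1.2), and Section 4.3 treats the week-13 sample as enough for the primary endpoint. A single A13 value in sampled patients carries no such bias. This stands, and it is why the point is conditional.

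Four further points stand in part:

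- The sum in 8.1 describes a comparison between arms, not a Cox covariate. It matters only if carried over to single patients.
- Blood is also drawn at surgery and at A1, so a reader who infers that early progressors have no post-vaccine immune data would be wrong. It is the responder rule that leaves those samples out.
- Patients with fewer than four post-surgery vaccines are replaced for the immunological endpoint (4.3), so the milder 0.60–0.72 may be the relevant range. But that set is not named for 12.1.6, and 4.3 keeps the replaced patients for efficacy.
- The exponential curve with median 17 months fits the newly diagnosed cohort poorly. With 13 patients, the chance of no event before 10 months is 2^(−130/17) = 0.5%. Early progression is supported mainly by the recurrent cohort; recurrent patients are eligible (3.1.2).

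Finally, 9.2 calls these endpoints unpowered and says that the data will be tabulated, and 12.1.6 sets no alpha. That limits the consequences. It does not remove a bias in the estimate, and 12.1.6 still commits to the model.

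**Conclusion.** The point holds in conditional form. The firm defect is that 12.1.6 leaves the covariate, its timing and the analysis set undefined while the clock starts at first treatment. If the 8.1 responder rule or a per-patient sum is used as a fixed covariate and some patients progress early, the PFS hazard ratio is biased towards benefit: about 0.43–0.59 in all treated and 0.60–0.72 with at least four post-surgery vaccines, at 50% responders.

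These sizes rest on the assumed response rate, confirmation times, A1 window and PFS patterns. The bias is zero if nobody progresses before 10 months. A reader might infer that the planned analysis is bound to show a false benefit; the documents do not support that, because the parameter is open and the amount of early progression is unknown. Nor should the sizes be carried over to OS. There the bias would act mainly through sampling that stops at progression, and it was not simulated. No primary result or arm comparison is affected.

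**What to change.** Amend 12.1.6 to define the parameter, name the analysis set and say how patients without the needed samples are handled. Then choose one of these:

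- **Time-dependent covariate (preferable for the two-visit rule).** A patient counts as a responder only from the date of the confirming sample. All events are kept, and the change is wording only.
- **Landmark at the visit where the parameter is complete.** Use A13 for a single A13 value, and A19 or A25 for the two-visit rule. Include only patients alive and progression-free then, count PFS and OS from that visit, and average rather than sum the samples up to it. At A19, patients confirmed only at A25 count as non-responders, which dilutes a real association but does not create a false one.

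No new visits, samples or patients are needed. The price of an A25 landmark is not small if early progression is common: it leaves out roughly one third to one half of the 24-month PFS events. Under the exponential patterns about 11 remain among 30 patients (for example 30 × (0.75 − 0.37) = 11.4). The time-dependent form or an earlier landmark is therefore the better choice. Neither cures the small sample, so the result should be reported as an estimate with its interval.

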12.2 Stopping Rule for Toxicity

The trial will be stopped for toxicity if the number of patients experiencing RLT in either arm is excessive. A probability of RLT (pRLT) exceeding 0.33 would be considered prohibitively high. Based on the previous experience in UPCI 07-057 and UPCI 08-135, we believe the expected pRLT is 1/20, and that the probability pRLT is equal to or greater than 0.33 is 0.05. We will use a continuous Bayesian beta-binomial monitoring rule: stop the trial if the estimated P(RLT>0.33)>0.33. We will use a beta prior distribution with

12 April 2020 Page 76 of 88 confidential

[figure not shown]
parameters α =0.09 and β =1.71, representing our beliefs above. The stopping rule is specified in the table.

# Patients	# RLT	# Patients	# RLT	
3	2	12	4	
4	2	13	5	
5	2	14	5	
6	3	15	5	
7	3			
8	3			
9	3			
10	4			
11	4			

Stopping rule for toxicity: for the given number of patients in the either arm, the trial is halted if the number of RLTs equals the given number

[figure not shown]
The operating characteristics of this rule were determined by Monte Carlo simulation and are displayed in the graph. It is seen that if the true pRLT>0.33, the expected number of patients enrolled is five and the probability the trial stops early is 0.75, but if the true pRLT=0.1, the probability the trial stops early equals 0.2.

12 April 2020 Page 77 of 88 confidential

Operating characteristics of the stopping rule. The blue line is the expected number of patients in the trial (left axis) and the red line is the probability the trial stops early (right axis) as a function of the true (unobserved) pRLT.

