4.1 Registration and Randomization

Eligible patients will be entered on study at UCSF by the Study Coordinators. All patients who sign the informed consent document will be registered in OnCore and the Brain Tumor Research Center Tissue Bank database.

Arm 1: Patients will receive IMA950- poly-ICLC vaccine plus varlilumab. **Arm 2**: Patients will receive IMA950- poly-ICLC vaccine alone.

The study is designed with a staggered safety lead-in with the first 3 patients assigned to Arm 2. The first 3 patients of the study will be enrolled in Arm 2 in a staggered manner as follows. After the first patient of the study is enrolled in Arm 2, Patient number 2 and 3 will not be enrolled until the previous patient receives 4 pre-surgery vaccines and recover from clinically indicated surgery for at least 6 weeks after surgery without a regimen-limiting toxicity (RLT) to confirm the safety of IMA950-poly-ICLC vaccine.

If any of the first 3 patients on Arm 2 shows a RLT (see definition in section 5.3), an additional 3 patients (patients 4, 5 and 6) will be enrolled in the same, staggered manner in Arm 2 while Arm 1 enrollment is held. If 2 or more of the patients on Arm 2 show a RLT, the arm will be considered intolerable and the study will be closed. If only one total of the 6 patients shows an RLT in Arm 2, the randomized design will be cancelled and the study will proceed with Arm 2 only to primarily evaluate the safety of the Arm 2 regimen. When the study is completed with the total evaluable 15 patients in Arm 2, we will review the safety data, and discuss with the FDA and IRB regarding the extension of the study to Arm 1.

If none of the first 3 patients treated on Arm 2 demonstrates a RLT, then 3 further patients will be enrolled in Arm 1 (with varlilumab) in the same staggered manner (subsequent patients will not be enrolled until the respective previous patient receives 4 pre-surgery vaccines and recover from clinically indicated surgery for at least 6 weeks after surgery without an RLT to confirm the safety of IMA950-poly-ICLC-varli treatment. If one of first 3 patients on Arm 1 shows a **Regimen Limiting Toxicity** an additional 3 patients will be enrolled in the same, staggered manner in Arm 1. If 2 or more of the patients on Arm 1 show a RLT, the arm will be considered intolerable.

12 April 2020 Page 27 of 88 confidential

If Arm 2 is tolerable but Arm 1 is not, then, the study will be carried out with Arm 2 only.

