5.6 Definition of Regimen Limiting Toxicities (RLT) and Suspension of Enrollment

5.6.1 Definition of RLT

Toxicity will be determined using the revised NCI Common Toxicity Criteria version 5.0 for Toxicity and Adverse Event Reporting (CTCAE) (http://ctep.info.nin.gov).

Management and dose modifications associated with the above adverse events are outlined in Section 5.7.

Participants will be observed for regimen limiting toxicity (RLT) throughout the study. The following are considered to be RLTs if they are judged possibly, probably or definitely associated with treatment. Should they occur, individual participants will be taken off study and no further injections will be given.

- Grade 2 or more any infusion reaction except for Grade 2 pain
- Grade 2 or more cytokine release syndrome
- Grade 2 or more bronchospasm or generalized uticaria (hypersensitivity)
- Grade 2 or more allergic reaction, such as exfoliative erythroderma, anaphylaxis, or vascular collapse
- Grade 2 or more autoimmune disease (e.g. hypothyroidism, autoimmune encephalitis)
- Any Grade 3 or more toxicity possibly, probably, or definitely related to the vaccine or Varlilumab with particular attention to the following events.

The following are also considered RLTs:

- Dosing delays > 6 weeks for IMA950+poly-ICLC vaccines or varillumab (Arm 1 patients only) administration.
- Delay of the scheduled surgical resection for longer than 2 weeks possibly, probably or definitely related to toxicity of the study treatment.

The following are NOT considered RLTs:

- Grade 3 nausea, vomiting, or diarrhea that resolves to ≤ grade 1 with or without treatment within 48 hours
- Grade 3 flu-like symptoms that resolve within 24 hours with the use of acetaminophen 650-1000 mg or with any NSAID

5.6.2 Events Which Will Temporarily Halt Enrollment at Any Time:

Certain events will be considered unacceptable and a single occurrence will lead to temporary closure of enrollment while under review for attribution to study therapy (not related to surgical procedures):

- The occurrence of grade 3 or 4 toxicity, excluding local skin reaction and flu-like symptoms in 3 patients
- Toxicity requiring the use of pressors, including grade 4 vascular leak syndrome or grade 3 and 4 hypotension
- Toxicity requiring ventilation support, including grade 4 respiratory toxicity

12 April 2020 Page 38 of 88 confidential

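### The operating characteristics stated for the toxicity rule are not those of its table, and 12.2 and 4.1 conflict when only Arm 1 crosses in its lead-in

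*Combined protocol and SAP*

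**What the plan says.** Section 12.2 uses a Beta(0.09, 1.71) prior for the RLT probability in continuous monitoring: "stop the trial if the estimated P(RLT>0.33)>0.33". It then presents a table, from 3 to 15 patients, as the specification of the rule, with the note "for the given number of patients in the either arm, the trial is halted if the number of RLTs equals the given number". The thresholds are 2 RLTs at 3 to 5 patients, 3 at 6 to 9, 4 at 10 to 12 and 5 at 13 to 15.

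Operating characteristics are reported from a Monte Carlo simulation shown in a graph. For true pRLT above 0.33, "the expected number of patients enrolled is five and the probability the trial stops early is 0.75"; for pRLT 0.1 the stop probability is given as 0.2. The text does not say whether these figures are per arm or for the whole trial. The graph's caption counts patients in the trial.

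Section 4.1 has its own lead-in rules. For Arm 2, any RLT in the first 3 patients means that "an additional 3 patients (patients 4, 5 and 6) will be enrolled in the same, staggered manner in Arm 2". For Arm 1, one RLT in the first 3 likewise leads to 3 more patients, and "If 2 or more of the patients on Arm 1 show a RLT, the arm will be considered intolerable". The consequence is then: "If Arm 2 is tolerable but Arm 1 is not, then, the study will be carried out with Arm 2 only".

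**The concern.** The three stated figures are what a safety committee or ethics board would use to judge how quickly the rule acts. Safety is a co-primary endpoint, so they should describe the rule that will be applied. They do not match the table, and each seems to fit a different calculation.

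The second issue is operational. The Arm 1 lead-in is there to detect toxicity of the varlilumab combination. If that arm alone crosses, one section ends the trial and the other continues it with Arm 2. Whoever applies the protocol on that day has no stated order of precedence.

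**Working it through.** **Inputs.** Prior, threshold, table and stated results are from 12.2. The maximum of 15 per arm is from 12.1.2 and matches the table's last row. Lead-in rules are from 4.1. Because pRLT above 0.33 is a range, I evaluate at its boundary and then move along it.

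**1. Reproduce the rule.** Prior mean = 0.09/(0.09+1.71) = 0.05, and P(p>0.33) = 0.0504, matching the stated beliefs of 1/20 and 0.05. After r RLTs in n patients the posterior is Beta(0.09+r, 1.71+n−r). The smallest r with posterior P(p>0.33) above 0.33 equals the printed threshold at all 13 sample sizes. The table is sound.

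**2. Exact operating characteristics.** Let f_n(r) be the probability of still running with r RLTs after n patients:

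f_n(r) = f_{n−1}(r)(1−p) + f_{n−1}(r−1)p, removing every r at or above the threshold for n.

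P(stop) is the total removed. E[N] is the sum over n of the probability of still running before patient n. For two arms, P(stop) = 1 − (1−P₁)(1−P₂).

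| Reading, 15 per arm | E[N] at 0.33 | P(stop) at 0.33 | P(stop) at 0.10 |
|---|---|---|---|
| Stated in 12.2 | 5 | 0.75 | 0.2 |
| Table, one arm | 7.8 | 0.76 | 0.11 |
| Table, either arm halts, equal rates | about 9.8 total (5.2 and 4.7 by arm) | 0.94 | 0.20 |
| Posterior formula from patient 1, one arm | 5.5 | 0.82 | 0.23 |
| Posterior formula from patient 1, two arms, equal rates | 4.8 total | 0.97 | 0.41 |

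Two-arm check for the table: 1 − (1−0.759)² = 0.942 and 1 − (1−0.106)² = 0.201. The two-arm totals assume alternating enrolment. Random 1:1 allocation gives 9.7 for the table, and the 4.1 lead-in order gives about 9.4.

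With Arm 1 at 0.33 and Arm 2 at 0.05, the table gives P(stop) = 1 − (1−0.759)(1−0.026) = 0.765, about 0.77, and a total of about 15 patients.

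**3. Move along the range.** For the table in one arm, E[N] falls to 5 only near pRLT 0.48, where P(stop) is 0.96. The 0.11 at pRLT 0.10 does not depend on that choice.

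**4. Formula against table at 1 and 2 patients.** The posterior P(p>0.33) is 0.54 for 1 RLT in 1 patient, 0.37 for 1 in 2 and 0.25 for 1 in 3. The formula is therefore met by one RLT in the first 1 or 2 patients, where the table has no entry. In the nearest reading at pRLT 0.10, 1 − 0.9² = 0.19 of the 0.23 comes from those two patients.

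**5. Section 12.2 against 4.1.** Take Arm 2 with no RLT in its first 3 patients, and Arm 1 with its second RLT at patient 3, 4 or 5. The 12.2 threshold (2 at 3 to 5 patients) is met, so the trial halts. Under 4.1 Arm 1 is intolerable and the study continues with Arm 2 only. At 2 RLTs in 6 Arm 1 patients the thresholds also differ: 4.1 calls the arm intolerable, while the table requires 3.

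For scale only, assume total RLT risks of 0.33 in Arm 1 and 0.05 in Arm 2, with a share f of each falling in a patient's lead-in window. Put r1 = 0.33f and r2 = 0.05f. The probability that Arm 2 passes and Arm 1 has 2 RLTs within its first 5 patients is

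(1−r2)³ × [3r1²(1−r1) + r1³ + 3r1(1−r1)² × (r1 + (1−r1)r1)].

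At f = 1 this is 0.857 × (0.255 + 0.147 + 0.098) = 0.43. At f = 0.75, 0.5 and 0.25 it is 0.30, 0.16 and 0.05. Of the 0.43, 0.857 × 0.33² = 0.09 is the case where both of Arm 1's first two patients have an RLT; 4.1 already applies there, but the table has no entry. The documents do not give f, and 5.6.1 says "Participants will be observed for regimen limiting toxicity (RLT) throughout the study".

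**The case against.** The strongest reply is that the three figures are round readings from a graph that is not available here, for an open range of pRLT. Read loosely, the one-arm posterior formula (5.5 / 0.82 / 0.23) is not far off. A smaller maximum brings it closer: with 12 patients it gives about 4.9 / 0.79 / 0.23. Started at patient 2, with a maximum of 9 and pRLT 0.35, it gives 4.4 / 0.75 / 0.22. This stands as a limit: a reading that fits may exist. But the documents give no maximum other than 15 per arm, and every such reading relies on stops that the table does not contain. So it does not rescue the figures as a description of the table.

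A second reply is that 12.2 makes the table the specification, so one RLT in 1 or 2 patients does not halt the trial, which agrees with the expansion in 4.1. That is right. The gap is a mismatch of wording between formula and table, not a separate operational failure.

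A third is that 4.1 naturally governs the lead-in and 12.2 the later phase. That is a reasonable intention, but neither section says so. The 12.2 table starts at 3 patients, the size of each lead-in cohort, and makes no exception for lead-in patients.

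**Conclusion.** The concern holds in two parts. With 15 per arm, the table does not yield 5 / 0.75 / 0.2 under either a one-arm or a two-arm reading. One arm matches the 0.75 but gives 7.8 patients and 0.11. Two arms at equal rates match the 0.2, and the five if counted per arm, but give 0.94. Separately, 12.2 and 4.1 prescribe opposite outcomes when only Arm 1 crosses at 3 to 5 patients. Confidence is high on both of these, and moderate on where the stated figures came from.

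Three stronger inferences are not supported:

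- A reader might conclude that true expected exposure is about ten patients rather than five. That needs the table and both arms at 0.33. With Arm 2 at 0.05 the total is about 15, and the formula in two arms at 0.33 gives about five. No single true figure is claimed.
- A reader might conclude that the rule stops less often than stated at 0.33. It does not: P(stop) is 0.76 to 0.97 across the readings in the table above.
- A reader might take it as shown that the sentence mixes one-arm and two-arm results. That is possible, but only the graph or code could show it.

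The probabilities of 0.05 to 0.43 for the conflicting path rest on assumed RLT rates and an assumed window share. The conflict itself is textual and needs neither.

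**What to change.** In 12.2, recompute and restate the operating characteristics for the table rule with both arms and the lead-in included. For each figure give the exact pRLT in each arm, and say whether patient counts are per arm or trial-wide. At least one scenario should have only Arm 1 at a high rate. Align the wording of the posterior rule with the table at 1 and 2 patients.

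Reconcile 4.1 and 12.2 on what happens when only Arm 1 crosses, including the different thresholds at 2 RLTs in 6 patients, and state which section takes precedence. Which one governs is for the sponsor to decide.

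The cost is a short simulation and a few sentences in two sections, with no extra patients.
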